#### **7.6.11 Other Events of Special Interest**

OEOSI will be summarized by treatment group for each category.

The following analyses will be conducted using the 100-day safety window:

- Overall summary of OEOSI by worst CTC grade (any grade, grade 3-4, grade 5) presented by Category / PT
- Overall summary of drug-related OEOSI by worst CTC grade (any grade, grade 3-4, grade 5) presented by Category / PT

By-subject listing of OEOSI will be provided.

### **7.6.12 Multiple Events**

The following summary tables will be provided:

- A table showing the total number and rate (exposure adjusted) of occurrences for all AEs.
- A table showing the total number and rate (exposure adjusted) of occurrences for AEs occurring in at least 5% of subjects in any treatment group.

In addition, the rate (exposure adjusted) and its 95% CI evaluated for different time intervals will be displayed graphically for each treatment group. This analysis will be limited to the rate of all AEs and all drug-related AEs. The analyses will be conducted using the 30-day safety window.

Listing displaying the unique instances of all AEs, i.e., after duplicates have been eliminated and overlapping and contiguous occurrences of the same event (i.e., same PT) have been collapsed will be provided. No formal comparisons will be made between treatment groups.

### **7.6.13 Laboratory Parameters**

The analysis population for each laboratory test is restricted to treated subjects who underwent that laboratory test. Laboratory tests (in addition to the tests specified below) with CTC criteria collected in the specific studies may also be included in the summaries.

### **7.6.14 Hematology**

The following will be summarized by treatment group as worst CTC grade on-treatment per subject and as shift table of worst on-treatment CTC grade compared to baseline CTC grade per subject: hemoglobin (HB), platelets, white blood counts (WBC), absolute neutrophils count (ANC) and lymphocyte count (LYMPH).

The analyses will be conducted using the 30-day safety window.

A by-subject listing of these laboratory parameters will be provided.

### **7.6.15 Serum Chemistry**

The following will be summarized by treatment group as worst CTC grade on-treatment per subject and as shift table of worst on-treatment CTC grade compared to baseline CTC grade per subject: ALT, AST, alkaline phosphatase (ALP), total bilirubin and creatinine.

The analyses will be conducted using the 30-day safety window.

A by-subject listing of these laboratory parameters will be provided.

### **7.6.16 Electrolytes**

The following will be summarized by treatment group as worst CTC grade on-treatment per subject and as shift table of worst on-treatment CTC grade compared to baseline CTC grade per subject: sodium (high and low), potassium (high and low), calcium (high and low), magnesium (high and low), and Glucose Serum (fasting hyperglycemia and hypoglycemia regardless of fasting status)

The analyses will be conducted using the 30-day safety window.

A by-subject listing of these laboratory parameters will be provided.

### **7.6.17 Additional Analyses**

In addition, further analyses on specific laboratory parameters will be performed by treatment group:

#### Abnormal Hepatic Function Test

The number of subjects with the following laboratory abnormalities from on-treatment evaluations will be summarized by treatment group:

- ALT or AST > 3 x ULN, > 5 x ULN, > 10 x ULN and > 20 x ULN
- Total bilirubin > 2 x ULN
- ALP > 1.5 x ULN
- Concurrent (within 1 day) ALT or AST > 3 x ULN and total bilirubin > 1.5 x ULN
- Concurrent (within 30 days) ALT or AST > 3 x ULN and total bilirubin > 1.5 x ULN
- Concurrent (within 1 day) ALT or AST > 3 x ULN and total bilirubin > 2 x ULN
- Concurrent (within 30 days) ALT or AST > 3 x ULN and total bilirubin > 2 x ULN The analyses will be conducted using the 30-day safety window.

A by-subject listing of these specific abnormalities will be provided.

#### Abnormal Thyroid Function Test

The number of subjects with the following laboratory abnormalities from on-treatment evaluations will be summarized by treatment group:

- TSH value > ULN and
  - with baseline TSH value  $\leq$  ULN
  - with at least one FT3/FT4 test value < LLN within 2-week window after the abnormal TSH test
  - with all FT3/FT4 test values  $\geq$  LLN within 2-week window after the abnormal TSH test
  - with FT3/FT4 missing within 2-week window after the abnormal TSH test
- TSH < LLN and
  - with baseline TSH value  $\geq$  LLN
  - with at least one FT3/FT4 test value > ULN within 2-week window after the abnormal TSH test
  - with all FT3/FT4 test values  $\leq$  ULN within 2-week window after the abnormal TSH test
  - with FT3/FT4 missing within 2-week window after the abnormal TSH test The analyses will be conducted using the 30-day safety window.

A by-subject listing of these specific abnormalities will be provided.

### **7.6.18 Vital Signs**

Vital signs collected on the CRF will be provided in separate listings.

### **7.6.19 Physical Measurements**

Physical measurements will be listed by subject.

### **7.6.20 Pregnancy**

By-subject listing of pregnancy tests results will be provided for randomized female subjects.

### **7.6.21 Adverse Events by Subgroup**

Overall summary of any AEs and drug-related AEs by worst CTC grade (any grade, grade 3-4, grade 5) presented by SOC/PT and for each treatment group for the following subgroups:

- Sex (Male vs. Female)
- Race
- Age (12 and < 18 vs ≥ 18 < 65 vs. 65 - < 75 vs. 75 - < 85 vs. ≥ 85 vs. ≥ 75 vs. ≥ 65)
- Region (Europe, North America, Rest of the World, Asia)

These analyses will be conducted using the 30-day safety window only.

### **7.6.22 Immunogenicity Analysis**

Further details on immunogenicity background and rationale, definitions, population for analyses and endpoints are described in [APPENDIX 3](#).

The number (%) of participants with the following anti-drug responses will be reported by dose, if applicable, and overall.

- Baseline ADA-positive
- ADA-positive
  - Persistent Positive (PP)
  - Not PP - Last Sample Positive
  - Other Positive
- ADA-positive with Neutralizing Positive
- ADA-negative

#### **Listing:**

All collected immunogenicity samples will be listed with flags indicating baseline-positive sample, ADA-positive sample or ADA-negative sample, together with the associated drug concentration.

#### **Clinical Implications:**

Clinical implications of positive ADA may be explored by a comparison of ADA-positive participants to ADA-negative participants.

Effect of immunogenicity on clearance of study drugs may be explored by comparison of clearance estimates (determined by PPK analysis), if appropriate. Effect of immunogenicity on safety will be explored by examining the frequency and type of AEs of special interest such as hypersensitivity/infusion reaction. Summary tables for incidence of each preferred terms and overall as a category of AEs will be provided, if the number of participants is of sufficient size (e.g., at least 10 participants). Otherwise, individual participant's safety profile will be examined and described based on a listing. Association between trough concentrations of study drugs and ADA assessments may be explored, as needed.

### **7.6.23 Electrocardiogram**

All of the available ECG parameter values, from each subject will be included in the ECG data set. All recorded ECG parameter values will be included in the data listings.

Baseline values are defined as the last recorded values prior to the first dosing. Although individual values for QT, QTcB, and QTcF will be presented in the data listings, only QTcF will be analyzed and discussed in the report. For other ECG parameters such as heart rate (HR), QT, QRS, and PR, summary measures (n, mean, standard deviation, median, minimum, and maximum) will be provided.

Analysis of Central Tendency: Summary statistics (n, mean, standard deviation, median, minimum, and maximum) will be presented for each ECG parameters and the corresponding changes from baseline by treatment and time point.

Listing:

- A by-subject listing of all ECG measures
- A listing of abnormal ECG interpretations

## **7.7 Pharmacokinetic Analyses**

The PK parameters and concentration data of relatlimab and nivolumab will be summarized and listed by study part, treatment, cycle, study day and time. All derived PK parameter values will be included in the PK dataset and reported, but only subjects with adequate PK profiles will be included in summary statistics and statistical analysis.

### **7.7.1 Pharmacokinetic Concentrations**

Summary:

Analyses for this section will be provided by the CPAR group.

Summary statistics will be provided for the following pharmacokinetic serum concentrations by treatment, cycle, study day and time for based on the relatlimab and Nivolumab PK Subjects.

- Serum concentrations of relatlimab
- Serum concentrations of Nivolumab

Listing:

- relatlimab and nivolumab serum concentrations

These data may also be pooled with other datasets for population PK analysis, which will be presented in a separate report.

The relationship of time with concentration will be investigated graphically (e.g., individual plots of change/percent change over time). Further analyses may be performed to characterize the relationship by fitting appropriate models (e.g., e-max model).

### **7.7.2 Ctrough and Ceo**

Ctrough and Ceo of BMS-986213 and Nivolumab will be tabulated by treatment, cycle and study day using summary statistics. To evaluate the steady state of relatlimab concentration in the body, the geometric means of Ctrough vs. cycle and day will be plotted. Ceo (end of infusion) and Ctrough will be listed, summarized and plotted by cycle and study day.

### **7.7.3 Population PK**

Population PK analysis and exposure-response analysis will be performed by CP&P, if needed. The concentration vs time data obtained in this study may be combined with data from other studies in the clinical development program to develop a population PK model. This model will be used to evaluate the effects of intrinsic and extrinsic covariates on the PK of relatlimab and to determine measures of individual exposure (such as steady-state peak, trough, and time-averaged concentration). Model determined exposures will be used for exposure-response analyses of selected efficacy and safety end points. Results of population PK and exposure-response analyses will be reported separately.

## **7.8 Biomarkers**

Analyses listed below may or may not be performed depending on data availability (additionally some analyses in the study may be subject to change as technologies and assay methods evolve). Additional types of analyses may be conducted on a post-hoc basis pending review of data. Not all analyses will be included in the Clinical Study Report (CSR) unless they represent meaningful findings or are relevant to subject management.

To describe any changes (or percent changes) in biomarkers, summary statistics of biomarkers and their corresponding changes (or percent changes) from baseline will be tabulated by planned timepoint and dose (i.e., treatment). The time course of these biomarker measures will be investigated graphically (e.g., individual plots of change/percent change from baseline vs. time. If there is any indication of exposure-response relationship, further analyses may be performed to characterize the relationship by fitting appropriate models (e.g., e-max model).

Analyses to assess the association of clinical efficacy and safety with selected markers in peripheral blood and tumor microenvironment, may be conducted on a hierarchical basis. If a biomarker measurement undergoes meaningful change over time, further analyses may be conducted to address additional hypotheses and explore relationship between the specific change and efficacy outcomes (as categorical or continuous variables) or safety events. The analysis

methods include methods specified in this SAP and additional exploratory methods not specified in the SAP upon review of the data.

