### **7.5.3 Subset Analyses of Progression-Free Survival**

The influence of baseline and demographic characteristics on the treatment effect among all randomized subjects will be explored via exploratory subset analyses. The median PFS based on KM product-limit method along with two-sided 95% CIs will be produced for the following subgroups:

- Subgroups in the following order: (Display 95% CI)
- OVERALL
- LAG3 STATUS AT BASELINE USING 1% CUTOFF ( $\geq 1\%$  vs  $< 1\%$ ) source: IRT
- LAG3 STATUS AT BASELINE USING 5% CUTOFF ( $\geq 5\%$  vs  $< 5\%$ ) source: IRT
- PD-L1 STATUS AT BASELINE USING 1% CUTOFF ( $\geq 1\%$  vs  $< 1\%$ /non-quantifiable) (Source: combination IRT and re-score)
- PD-L1 STATUS AT BASELINE USING 5% CUTOFF ( $\geq 5\%$  vs  $< 5\%$ /non-quantifiable) (Source: combination IRT and re-score)
- PD-L1 STATUS AT BASELINE USING 10% CUTOFF ( $\geq 10\%$  vs  $< 10\%$ /non-quantifiable) (Source: combination IRT and re-score)
- INTERACTION OF LAG-3 EXPRESSION AND PDL-1 STATUS (Source: combination IRT and re-score)
- Subjects with LAG-3  $\geq 1\%$  and PD-L1  $\geq 1\%$
- Subjects with LAG-3  $\geq 1\%$  and PD-L1  $< 1\%$  (or non-quantifiable)
- Subjects with LAG-3  $< 1\%$  and PD-L1  $\geq 1\%$
- Subjects with LAG-3  $< 1\%$  and PD-L1  $< 1\%$  (or non-quantifiable)
- BRAF MUTATION STATUS (BRAFF MUTANT; BRAFF WILDTYPE) source: IRT
- AJCC STAGE (M0/M1any[0] ; M1any1) (use RAVE database – combination of CRF variable metastasis and lab data for LDH).
- BASELINE METASTASIS STAGE: (source: CRF variable metastasis and lab data for LDH)
- M0
- M1a (programming notes M1a= M1a, M1a(0) LDH not elevated, M1a(1) LDH elevated)
- M1b (programming notes M1b= M1b, M1b(0) LDH not elevated, M1b(1) LDH elevated)
- M1c (programming notes M1c= M1c, M1c(0) LDH not elevated, M1c(1) LDH elevated)
- M1d (programming notes M1d= M1d, M1d(0) LDH not elevated, M1d(1) LDH elevated)
- DISEASE STAGE AT STUDY ENTRY (III vs IV)

- HISTOLOGY (DISEASE SUBTYPE) Four categories: cutaneous acral, cutaneous non-acral, mucosal, and other
- BASELINE LDH ( $\leq$  ULN;  $>$  ULN)
- BASELINE LDH ( $\leq$  2x ULN;  $>$  2x ULN)
- HISTORY OF BRAIN METASTASES (YES, NO) from disease history CRF page
- TUMOR BURDEN AT BASELINE PER BICR and per INV ( $<$ Quartile 1, quartile 1 to  $<$ Quartile 3 and  $\geq$ Quartile 3)
- BASELINE ECOG PS (0, 1) from CRF
- SMOKING STATUS (CURRENT/FORMER, NEVER SMOKED)
- AGE CATEGORIZATION:
  - $\geq$  12 and  $<$  18
  - $\geq$  18 and  $<$  65

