  - $\geq$  65 and  $<$ 75
  - $\geq$ 65
  - $\geq$ 75
- SEX (MALE, FEMALE)
- RACE (WHITE, BLACK OR AFRICAN AMERICAN, ASIAN, AND OTHER)
- REGION (USA/Canada, Europe, Latin America (Central/South America), Australia/NZ)

A forest plot of the PFS hazard ratios (along with the 95% CIs) will be produced for each level of the subgroups listed above. An analysis will be conducted if the number of subjects in the subgroup category is more than 10.

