#### **7.8.5.1 PD-L1 and Lag-3 Expression**

Analyses of PD-L1 and LAG-3 expression (PDL-1/LAG-3) are descriptive in nature and intended to examine the distribution of PD-L1 and/or LAG-3 expression and assess potential associations between PD- L1/LAG- 3 expression and efficacy measures. If there is an indication of a meaningful association, future work will evaluate PD- L1/LAG- 3 expression as a predictive biomarker, including selection of an optimal PD- L1/LAG- 3 expression cut-off to classify subjects as PD- L1/LAG- 3 positive or PD- L1/LAG- 3 negative.

PD-L1/LAG-3 expression in this section will be defined based on the validated immunoassay method for PD- L1/LAG- 3 IHC assays. PD- L1/LAG- 3 status is a categorical variable by X% cut off for quantifiable PD-L1/LAG-3 expression:

- Positive:  $\geq X\%$  PD- L1/LAG-3 expression
- Negative:  $< X\%$  PD- L1/LAG-3 expression

where X denotes the possible PD- L1 expression levels 1%, 5% and 10% cutoff levels and LAG-3 expression cut-off values of 1%, 5%. Additional cut off values may also be explored, but the 1% cutoff for PD- L1/LAG- 3 will be considered primary.

Analyses of PD- L1/LAG- 3 will include:

- Examine the distribution of PD- L1/LAG-3 expression
- Assess potential association between PD- L1/LAG-3 status and efficacy measures
- Evaluate the potential predictive relationship of the PD- L1/LAG- 3 status and efficacy measures
- Test performance statistics such as sensitivity, specificity, positive predictive value (PPV) and negative predictive value (NPV)
- Assess potential association between PD- L1/LAG-3 status and overall AEs

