A Cox proportional hazards regression model will be fitted for PFS with treatment, PD-L1 status, LAG-3 status, PD-L1\*LAG-3 status, and treatment by PD-L1/LAG-3 status interaction. Although the study is not designed to have substantial power to formally test the interaction of the model, an interaction test at significance level of 0.2 will warrant further exploration and the following statistics will be reported:

- Interaction p-value
- Hazard ratio of treatment vs. control and its associated 95% CI for each of the PD-L1/LAG-3 status subgroup

- Hazard ratio PD-L1/LAG-3 positive vs. negative and its associated 95% CI within each treatment group. For the combination of the two biomarkers, we will designate one of the four cells to be the reference group(the PD-L1-/LAG-3-) and report the ratio of the hazard ratios

Analyses for OS endpoint:

A Cox proportional hazards regression model will be fitted for OS with treatment, PD- L1 status, LAG-3 status, PD-L1\*LAG-3 status, and treatment by PD-L1/LAG-3 status interaction. Although the study is not designed to have substantial power to formally test the interaction of the model, an interaction test at significance level of 0.2 will warrant further exploration and the following statistics will be reported:

- Interaction p-value
- Hazard ratio of treatment vs. control and its associated 95% CI for each of the

PD- L1 status subgroup

- Hazard ratio PD-L1/LAG-3 positive vs. negative and its associated 95% CI within each treatment group. For the combination of the two biomarkers, we will designate one of the four cells (the PD-L1-/LAG-3-) to be the reference group and report the ratio of the hazard ratios.

Analyses for ORR endpoint:

A logistic regression model will be fitted for response (yes=CR or PR, No=SD or PD or unknown) with treatment, PD-L1/LAG-3 status and the treatment by PD-L1/LAG-3 status interaction. Although the study is not designed to have appropriate power to formally test the interaction of the model, an interaction test at significance level of 0.2 will warrant further exploration and the following statistics will be reported:

- Interaction p-value
- Odds ratio of treatment vs. control and its associated 95% CI will be reported for each of the PD-L1/LAG-3 status subgroup

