## **9 CONTENT OF REPORTS**

All analyses described in this SAP will be included in the Clinical Study Report(s) except where otherwise noted. Refer to the Data Presentation Plan for mock-ups of all tables and listings.

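### SAP 7.8 lets exploratory biomarker analyses into the study report on the strength of their own results, and the 0.2 interaction sentence in SAP 7.8.5.2 can be read the same way

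*SAP*

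**What the plan says.** SAP 9 sets the general rule: "All analyses described in this SAP will be included in the Clinical Study Report(s) except where otherwise noted". SAP 7.8 is such an exception. For the analyses listed under it: "Not all analyses will be included in the Clinical Study Report (CSR) unless they represent meaningful findings or are relevant to subject management". It also provides: "Additional types of analyses may be conducted on a post-hoc basis pending review of data". Neither inclusion criterion is defined. SAP 4.3.2 offers a separate report, but only as a possibility and only for measures not available in time for the study report.

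For PD-L1 and LAG-3, SAP 7.8.5.1 says the analyses "are descriptive in nature and intended to examine the distribution of PD-L1 and/or LAG-3 expression" and assess association with efficacy. SAP 7.8.5.2 then fits interaction models for PFS, OS and ORR. For PFS and OS it concedes that "the study is not designed to have substantial power to formally test the interaction of the model", with near-identical wording for ORR. It continues: "an interaction test at significance level of 0.2 will warrant further exploration and the following statistics will be reported". The list that follows holds the interaction p-value, treatment effects by marker status, marker-positive versus marker-negative ratios within each arm, and the ratio of hazard or odds ratios.

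Separately, SAP 7.5.3 lists LAG-3 at two cut-offs, PD-L1 at three, and the four PD-L1 by LAG-3 cells, and states: "A forest plot of the PFS hazard ratios (along with the 95% CIs) will be produced for each level of the subgroups listed above". SAP 7.5.5 and 7.5.8 do the same for OS and ORR.

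**The concern.** Whether a biomarker analysis is meaningful can be decided only by looking at it. A rule that uses this as its entry criterion lets null results drop out of the report while positive ones stay, and the open post-hoc allowance means that the set of analyses can also be chosen after the data are seen. Nothing requires the report to say how many markers, cut-offs or endpoints were examined. Benjamini-Hochberg control is specified only for the Phase 2 subgroup comparisons (SAP 5.1.1, 5.1.2 and Table 7.5-1), and the study went on to Phase 3.

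The use to which these results will be put gives this weight. Relating biomarkers to efficacy is a stated exploratory objective (Protocol Table 4-1, SAP Table 3-1). Protocol 5.4.6 expects the analyses to identify predictive markers and to separate those for monotherapy from those for the combination. SAP 7.8.5.1 makes an indication of a meaningful association the trigger for later work on a cut-off. If what is shown has been filtered on its size, that later work starts from estimates that are too large.

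**Working it through.** **1. Which analyses does the filter reach, and are they promised elsewhere?**

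| Analysis | SAP section | Commitment | Planned unfiltered elsewhere? |
|---|---|---|---|
| Flow cytometry | 7.8.1 | Summaries; links with response, PFS and AEs optional | No |
| Soluble factors | 7.8.2 | As flow cytometry | No |
| Gene expression | 7.8.3 | Optional summary, no endpoint named | No |
| Mutation burden | 7.8.4 | Optional association with outcome | No |
| Other IHC markers | 7.8.5 | Figures annotated with response | No |
| PD-L1/LAG-3 treatment effects by status | 7.8.5.2 | Planned | Yes: 7.5.3, 7.5.5, 7.5.8 |
| PD-L1/LAG-3 interaction p-value, positive-versus-negative ratios within arm, ratio of hazard or odds ratios | 7.8.5.2 | Planned, after the 0.2 sentence | No |

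The 7.5 sections lie outside 7.8, so SAP 9 puts them in the report; their only condition is a minimum subgroup size.

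**2. Two readings of the 0.2 sentence.** It can mean (a) report the list, and explore further if p < 0.2, or (b) report the list only if p < 0.2. The wording does not settle which. The rest sizes reading (b).

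**3. Inputs.** 365 PFS events, HR 0.73, about 85% power, two-sided 0.05 and 1:1 allocation (SAP 5.2, 5.2.1); 300 deaths (SAP 5.2.1); 0.2 taken as two-sided, since SAP 7.5 reports two-sided p-values. Assumed: one binary marker with prevalence p, and events split in proportion to prevalence. The range for p is an assumption: 25-50% for the null case, and 30-65% otherwise, which spans the PD-L1 positivity rates in SAP 6.2.1 (30-40% as first scored, 55-65% historically).

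**4. Check on the event count.** √365/2 × |ln 0.73| − 1.96 = 3.006 − 1.96 = 1.046, so power is 0.852, agreeing with the stated 85%. The plan gives no figure for the power of the interaction test.

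**5. Standard error.** SE(log ratio of hazard ratios) = (2/√365)/√(p(1−p)) = 0.1047/√(p(1−p)). At p = 0.50 this is 0.209; at p = 0.25 it is 0.242.

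**6. Size of what is shown under (b) with no true interaction.** The critical value is 1.2816. The mean of |Z| given |Z| > 1.2816 is 2φ(1.2816)/0.2 = 1.755.

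- p = 0.50: 1.755 × 0.209 = 0.367, a ratio of 1.44.
- p = 0.25: 1.755 × 0.242 = 0.424, a ratio of 1.53.
- Without selection the mean of |Z| is √(2/π) = 0.798, giving ratios of 1.18 and 1.21.
- At 300 deaths the selected figures are 1.50 and 1.60.

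Each ratio could equally be its inverse.

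**7. Under (b) with a true interaction** (365 PFS events, p from 0.30 to 0.65):

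| True ratio | Chance of p < 0.2 | Mean shown size ÷ true size, log scale |
|---|---|---|
| 0.8 | 0.39-0.42 | 1.9-2.0 |
| 0.7 | 0.61-0.67 | 1.3-1.4 |
| 0.6 | 0.83-0.88 | 1.1 |

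**8. Chance that at least one of PFS, OS and ORR passes 0.2 with no interaction.** If independent, 1 − 0.8³ = 0.488. By simulation with correlation 0.5, 0.7 and 0.9 it is 0.43, 0.38 and 0.30.

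**The case against.** The strongest reply is that the most important biomarker evidence is already safe. Treatment effects by PD-L1 and LAG-3 status, including the four combined cells, are planned for PFS, OS and ORR with no p-value condition, and no selection effect applies to them. The analyses are labelled descriptive, low interaction power is disclosed, choice of a cut-off is left to future work, and SAP 5.2.1 says that endpoints outside the hierarchy are not formally tested. All of this stands and limits the point. It does not remove it: a descriptive table misleads when null rows are left out, and the 7.5 forest plots contain none of the other markers and none of the interaction statistics that separate a predictive marker from a prognostic one.

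Four stronger readings are tempting, and the documents do not support them.

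- A reader might infer that the 0.2 level is a definite condition for reporting. The sentence is ambiguous, and reading (a) is just as natural, since the interaction p-value itself heads the list.
- A reader might infer that every marker is tested against PFS, OS, ORR and adverse events. For most markers outside PD-L1/LAG-3 the SAP only permits exploration; models for all three efficacy endpoints are specified for PD-L1/LAG-3 alone.
- A reader might attach a programme-wide false-positive rate, such as 1 − 0.95²⁰ = 64% for 20 independent tests. The SAP gives no count of tests and does not equate meaningful with p < 0.05.
- A reader might take meaningfulness as the only route into the report. Relevance to subject management is a second one.

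**Conclusion.** The concern holds in a limited form. Followed as written, SAP 7.8 permits the reported associations for flow cytometry, soluble factors, gene expression, mutation burden and other IHC markers to be chosen on their results, for a stated objective. The size of that risk cannot be computed from the documents. For the PD-L1/LAG-3 interaction statistics the problem is an ambiguous sentence. Under its restrictive reading and no true interaction, the mean ratio of hazard ratios among those shown would be about 1.44 to 1.53, or its inverse, against 1.18 to 1.21 without selection.

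Those figures rest on one binary marker, events proportional to prevalence and a one-degree-of-freedom test. The model in the SAP contains both markers and their product, and would be less precise. The inflation shrinks as the true interaction grows, to about 1.1 times on the log scale at a true ratio of 0.6.

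Exaggeration is therefore a risk that the rule allows, not a result that the documents establish, and it does not extend to the biomarker evidence as a whole. The primary and key secondary tests and alpha are untouched.

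**What to change.** Two changes of wording.

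1. In SAP 7.8, replace the inclusion sentence with a rule that every biomarker analysis performed is reported, or at least listed with its result, in the study report or a named biomarker report, whatever that result is. The report should state how many markers, cut-offs and endpoints were examined and mark post-hoc analyses as such.
2. In SAP 7.8.5.2, state that the interaction-model statistics for PFS, OS and ORR are reported whatever the p-value, and that the 0.2 level serves only to trigger further exploration.

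The cost is a longer appendix or a separate biomarker report. No new data are needed and no planned test changes.
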